Title of the study: Rehabilitative Trial With Cerebello-Spinal tDCS in Neurodegenerative Ataxia

NCT number: NCT03120013

Date: January 21, 2016

Standard Protocol Approvals, Registrations, and Patient Consents

Full written informed consent was obtained from all participants according to the Declaration of Helsinki. The study protocol was approved by the local ethics committee (Brescia Hospital), #NP1576 approved 01.21.16. This trial has been registered at ClinicalTrials.gov (NCT03120013).

Primary research questions/classification of evidence

Our primary research question was to determine whether cerebellar anodal tDCS and spinal cathodal tDCS could improve symptoms and modulate cerebello-cerebral connectivity in patients with ataxia, at short and long-term.

Participants

Twenty-one patients with neurodegenerative ataxia, respectively seven patients with spinocerebellar ataxia (SCA) type 2,¹ six with the cerebellar variant of multiple system atrophy (MSA-C),² one with SCA38,³ one with SCA14,⁴ one with Friedreich's ataxia,⁵ one with Ataxia with Oculomotor Apraxia (AOA) type 2,⁶ four with sporadic adult-onset ataxia,⁷ were recruited from the Centre for Ageing Brain and Neurodegenerative Disorders, Neurology Unit, University of Brescia, Italy and entered the study. One patient with MSA-C dropped out from the study during the first round (sham stimulation) and was not considered in the present analysis.

The number of included patients, corrected for possible drop-outs and patients in which a reliable motor cortex could not be elicited, was assessed using a power analysis, from results obtained from previous studies.⁸

Each patient fulfilled current clinical criteria and genetic trait for the specific diagnosis. All enrolled patients shared a cerebellar syndrome and, as assessed by MRI, had quantifiable cerebellar atrophy. For each patient, a review of past medical history, a semi-structured neurological examination and a standardized assessment of cerebellar functions was carried out.

Patients were evaluated free of sedative drugs or sodium- or calcium-channel blockers to avoid any interaction with the presumed neuromodulatory effects of tDCS.

In addition, ten age-matched healthy control subjects were recruited as reference group for TMS parameters.

Study design

Patients were randomized into two groups: each group received anodal cerebellar tDCS and cathodal spinal tDCS (real tDCS) or sham stimulation for 5 days/week for 2 weeks, in a 1:1 ratio respectively.

At baseline, each patient underwent a clinical evaluation, according to a standardized assessment (see below, clinical assessment), and CBI evaluation using Transcranial Magnetic Stimulation (TMS) (see below, CBI assessment) (pre-stimulation, T0). The same assessments were carried out after two-weeks of either real or sham tDCS (post-stimulation, T1), at one-month (T2) and at three-months follow-up (T3).

After a wash-out period of three months after the last visit (i.e., T3), each patient received the opposite treatment (cross-over phase), and underwent the same standarized assessment as in the first phase, at baseline, at two-weeks post-stimulation, at one-month and at three-months (see **Fig 1**).

Six principal investigators were involved: one performing the clinical evaluation ([name]), one performing CBI at baseline and at follow-up ([name]) and four performing tDCS ([name], [name], [name], [name]). The patient and the examiners performing clinical ratings and TMS protocols were blinded to the type of stimulation.

Clinical assessment

At each time-point, the Scale for the Assessment and Rating of Ataxia (SARA)⁹ and the International Cooperative Ataxia Rating Scale (ICARS)¹⁰ were employed to evaluate cerebellar deficits.

SARA consists of eight items, including gait, stance, sitting, speech disturbance, finger chase, nose-finger test, fast alternating hand movements, and heel-shin slide. The higher the score, the worse is the patient's performance. ICARS is a semiquantitative 100-point scale consisting of 19 items, divided into four weighted sub-scores, namely posture and gait disturbances, limb kinetic function, speech disorder, and oculomotor deficits.

To evaluate finger dexterity and upper limb coordination, four timed trials of the 9-hole peg test (9HPT)¹¹ were performed separately for each hand. The 9HPT is a commonly used test to assess finger dexterity: the patient picks the pegs one at time and puts them in nine holes on a peg board until all holes are filled and then removes them one at a time, as quickly as possible. The total time to complete the task is recorded for each trial and for each separate hand (dominant and non-dominant).

To assess gait speed, we performed, four times for each session, the 8-meter walking time (8MW),¹² defined as the time needed to walk 8 meters "as quickly as possible but safely", with any device but without help of another person or wall.

Finally, the Italian version of the Short-Form Health Survey 36 (SF-36), an interview-administered self-reported scale consisting of 36 scaled scores assessing 8 subdomains (vitality, physical functioning, bodily pain, general health perceptions, physical role functioning, emotional role functioning, social role functioning, mental health, communication, psychosocial and energy), was used to assess changes in the patient's quality of life.¹³

Cerebellar Brain Inhibition (CBI)

TMS was performed with two figure-of-eight coils (each loop diameter 70 mm) connected to two Magstim stimulators (Magstim Company, Oxford, UK). The magnetic stimuli had a monophasic

current waveform (rise time of 100 μ s, decaying back to zero over 800 μ s). Motor evoked potentials (MEPs) were recorded from the right first dorsal interosseous muscle (FDI) through surface Ag/AgCl electrodes placed in a belly-tendon montage and acquired using a Biopac MP-150 electromyograph (BIOPAC Systems Inc., Santa Barbara, CA, USA).

The TMS coil was held tangentially over the scalp region corresponding to the primary hand motor area contralateral to the target muscle, with the coil handle pointed 45° posteriorly and laterally to the sagittal plane. The motor hot spot was defined as the location where TMS consistently produced the largest MEP size at 120% of the resting motor threshold (rMT) in the target muscle and was marked with a felt tip pen on the scalp to ensure constant placement of the coil throughout the experiment.

rMT was defined as the minimal stimulus intensity needed to produce MEPs with an amplitude of at least 50 μ V in 5 out of 10 consecutive trials during complete muscle relaxation, which was controlled by visually checking the absence of EMG activity at high-gain amplification ¹⁴.

CBI was assessed using previously described techniques ¹⁵⁻¹⁷. Briefly, the second coil was used to deliver the conditioning stimuli (CS) which was placed over the contralateral cerebellar hemisphere ¹⁸ (1 cm inferior and 3 cm right to the inion), a site corresponding to the posterior and superior lobules of the lateral cerebellum ¹⁹. For cerebellar stimulation, the handle was positioned upward with the coil placed tangentially to the skull (see **Fig. 1**). The cerebellar CS intensities were set at 90% rMT obtained in the ipsilateral motor cortex ¹⁷. CS preceded the target stimuli (TS) by different interstimulus intervals (ISIs) ranging from 3 to 10 ms (3, 5, 10 ms). There were four conditions, corresponding to the three different ISI and the TS alone. Ten responses were collected for each different ISI and fifteen for the TS alone in a pseudorandomized sequence. The amplitude of the conditioning MEPs was expressed as a ratio of the mean unconditioned response. The inter trial interval was set at 5 sec ($\pm 10\%$).

Transcranial direct current stimulation

tDCS was delivered by a battery-driven constant current stimulator through a pair of saline-soaked (0.9% NaCl) surface sponge electrodes ($7 \times 5 \text{ cm}^2$, current density 0.057 mA/cm^2 for the anodal cerebellar electrode; $8 \times 6 \text{ cm}^2$, current density 0.041 mA/cm^2 for the cathodal spinal electrode). The anode was placed on the scalp over the cerebellum area (2 cm under the inion) and the cathode over the spinal lumbar enlargement (2 cm under T11) (see **Fig. 1**). The electrodes were secured using elastic gauzes and an electroconductive gel was applied to electrodes to reduce contact impedance ($<5 \text{ k}\Omega$ for all sessions).

During anodal stimulation a constant current of 2 mA was applied for 20 minutes, as suggested by recently published consensus recommendations^{20,21} and on the basis of computation modeling studies.^{22,23}

For the sham condition, the electrode placement was the same, but the electric current was ramped-down 5 seconds after the beginning of the stimulation to make this condition indistinguishable from the experimental stimulation. To detect differences in the perception of the stimulation, we asked the patients whether they thought they were receiving real or sham stimulation at the end of the two-weeks' treatment.

Statistical Analyses

To assess the effect of tDCS treatment on clinical scores over time we used a two-way repeated measure ANCOVA with TIME (T0, T1, T2 and T3) and TREATMENT (sham vs real stimulation) as within-subjects factors, and the sequence in which stimulation was performed (real-sham vs sham-real) as covariate.

To assess the effect of tDCS treatment on CBI we used a three-way repeated measures ANCOVA with TIME (T0, T1, T2 and T3), ISI (3, 5, 10 ms) and TREATMENT (sham vs real stimulation) as within-subject factors, and the sequence in which stimulation was performed (real-sham vs sham-real) as covariate.

When a significant main effect was reached, *post hoc* tests with Bonferroni correction for multiple comparisons were conducted to analyze group-differences at respective ISIs or time points. Mauchly's test was used to test for assumption of sphericity, while Greenhouse–Geisser epsilon determination was used to correct in case of sphericity violation.

Spearman's rank-order correlations were used to assess associations between the improvement in functional scores, neurophysiological parameters and demographic or clinical characteristics. Statistical analyses were performed using SPSS version 21 (SPSS, Inc., Chicago, IL, USA).

References

6. Moreira M-C, Klur S, Watanabe M, et al. Senataxin, the ortholog of a yeast RNA helicase, is mutant in ataxia-ocular apraxia 2. *Nat Genet*. 2004;36(3):225-227. doi:10.1038/ng1303.

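### Does leaving out the one patient who dropped out, under an ANCOVA that needs complete patients, call for a mixed model on all randomised patients?

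*Combined protocol and SAP*

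**What the plan says.** Participants lists 21 patients with ataxia who entered the study and reports one loss: "One patient with MSA-C dropped out from the study during the first round (sham stimulation) and was not considered in the present analysis". Further on, that section says that a power analysis fixed the sample size, with an allowance for losses: "The number of included patients, corrected for possible drop-outs and patients in which a reliable motor cortex could not be elicited". It gives no drop-out rate, effect size, alpha or power.

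Study design describes a two-round cross-over with four visits per round (T0 to T3). On T0 it says "At baseline, each patient underwent a clinical evaluation, according to a standardized assessment", and on the second round "After a wash-out period of three months after the last visit (i.e., T3), each patient received the opposite treatment (cross-over phase".

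Statistical Analyses names two models. For clinical scores the wording is: "two-way repeated measure ANCOVA with TIME (T0, T1, T2 and T3) and TREATMENT (sham vs real stimulation) as within-subjects factors". For CBI the interstimulus interval joins the within-patient factors: "three-way repeated measures ANCOVA with TIME (T0, T1, T2 and T3), ISI (3, 5, 10 ms) and TREATMENT (sham vs real stimulation". Both models carry stimulation sequence as a covariate, with Mauchly's test and the Greenhouse–Geisser correction, in SPSS 21. The plan gives no missing-data rule, no definition of the analysis set and no sensitivity analysis.

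**The concern.** A randomised patient is removed after allocation, during an assigned round, and the named method would by default remove anyone else with a gap. A classical repeated-measures model needs all 8 visits per patient for a clinical score and all 24 cells for CBI. That complete-patient behaviour is inferred from the method; the plan does not state it. The schedule runs for at least nine months (three of follow-up, three of wash-out, three of follow-up), so missed visits are plausible. The sample size allowed for drop-outs in words, while the analysis says nothing about them.

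Three things would be at stake: the principle of analysing everyone randomised, the loss of whole patients over single missed visits, and a borderline result that turned on one patient. A REML mixed model using all observed visits is the usual remedy and needs no new data.

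**Working it through.** **Counts (Participants, Study design, Statistical Analyses).** Diagnoses: 7 + 6 + 1 + 1 + 1 + 1 + 4 = 21, so 20 are analysed and 1/21 = 4.8% excluded. Planned visits: 21 × 8 = 168. CBI cells: 4 × 3 × 2 = 24. The plan's sample size cannot be reproduced, because its inputs are not given.

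**What the drop-out can contribute to the T1 effect.** The target is the real-minus-sham difference in change from T0 to T1. Let s² be the variance of one such change, with changes in the two rounds independent once the patient effect cancels.
- 20 complete patients: variance s²(1/20 + 1/20).
- Adding a patient with sham T0 and T1 only: variance s²(1/20 + 1/21).
- Effective patients: 2/(1/20 + 1/21) = 20.488, a gain of 0.49. Standard error ratio √(20/20.488) = 0.988, that is 1.2% smaller.

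With period effects allowed to differ by visit, each round contributes n₁n₂/(n₁ + n₂), where n₁ and n₂ are the numbers on real and sham in that round.
- Completers split 10/10: 2 × (10·11/21 + 10·10/20) = 2 × (5.238 + 5) = 20.476, a gain of 0.48.
- Completers split 11/9, with the drop-out joining the smaller group: from 2 × (4.95 + 4.95) = 19.80 to 2 × (11·10/21 + 4.95) = 20.376, a gain of 0.58 and a standard error 1.4% smaller. The split is not given.

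**Less favourable cases.** These come from generalised least squares with 10 + 10 completers. Assumed patient / patient-by-period / residual shares are 85/5/10, 70/10/20 and 50/10/40, with AR(1) correlation 0, 0.5 or 0.8 within a round. The gain is 20 × var(20)/var(21) − 20.

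| Sham visits observed | T1 change | T3 change |
|---|---|---|
| T0 only | 0.005–0.093 | 0.01–0.09 |
| T0, T1 | 0.49 | 0.12–0.15 |
| T0, T1, T2 | 0.49 | 0.16–0.29 |

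With T0 only, the standard error for T1 falls by 0.01–0.23%. If patients repeat their own visit pattern in both rounds (variance half the residual), the 0.49 with T0 and T1 observed falls to 0.14–0.32.

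**Whether those visits exist.** The patient's T0 is inferred from the statement that each patient was assessed at baseline. The same section says each patient crossed over, which is untrue of the drop-out, so its wording may describe completers. If no T0 was kept, the gain is zero.

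**Influence of one patient.** Suppose the 20 show a paired effect of 0.5 SD: t = 0.5 × √20 = 2.24, p = 0.038. A 21st paired difference of zero leaves p = 0.038, and an equal and opposite one gives p = 0.051. The drop-out has no real round, so no such difference was observed and a mixed model would not supply one.

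**Other missed visits.** If each visit were missed independently with probability m, complete patients would number 20(1 − m)⁸: 17.0 at m = 2% and 13.3 at m = 5%. Both rates are assumptions; the documents report no missed visit among the 20.

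**Price of the substitute.** Simulated type I error at nominal 5% (shares 70/10/20, no effect, REML with Satterthwaite degrees of freedom):
- Random patient and patient-by-period effects only: 9.6% and 13.1% for T3 at AR(1) 0.5 and 0.8.
- CBI without a patient-by-visit effect: 11.2% and 18.0% for T1, with a session effect of 25% and 50% of within-round variance.
- One unstructured 4×4 matrix common to both rounds: 5.4–5.7%, but 1.7–2.4% (standard error about 21–22% too large) when a shared visit pattern exists.
- Adding a shared patient-by-visit effect restores 5.5% in that case. The CBI model with all these components together was not simulated.

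**Fixed effects.** Sequence as a between-patient covariate normally interacts with TIME and TREATMENT, and that three-way term is period × visit. A mixed model with period and sequence as main effects only would lose it. If the T0–T1 change differs by d between rounds, the bias in the T1 contrast is (11 − 9)/20 × d = 0.10d with an 11/9 split, or (10/20 − 10/21) × d = 0.024d with 10/10 plus the drop-out's T0 and T1.

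**The case for a change.** The best case for changing the plan is one of principle. An all-randomised set removes a discretionary exclusion and costs SAP wording and a standard procedure. The planned ANCOVA could stay alongside, and any patient with one missed visit would keep the other seven. The pitfalls of the mixed model can also be largely avoided by stating a suitable covariance and including period × visit.

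Much of this stands as general practice. The exclusion is real, no missing-data rule is written, and a well-specified mixed model held its error rate for clinical scores in simulation. What does not stand is a gain for this trial. Further missingness is hypothetical on the documents' account. With T0 alone, analysing all 21 is close to nominal. The missing-at-random assumption is also doubtful where incompleteness would be most likely: the 8-meter walk must be done "with any device but without help of another person or wall", so a missing time may itself mean a worse state. For CBI, "The amplitude of the conditioning MEPs was expressed as a ratio of the mean unconditioned response" means the three intervals share one denominator at each session, which adds a further covariance component at the same sample size. Patients without an elicitable motor response cannot be recovered by any model.

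**Conclusion.** No change to the plan follows. The factual observations are correct: one of 21 patients is left out, and the named ANCOVA by default uses complete patients. The effect on the treatment comparison is negligible: under 0.1 effective patients if only T0 was recorded, 0.14–0.32 for the T1 change if T1 was reached and patients share a visit pattern, and about half a patient at best (0.49, or 0.58 with an 11/9 split). Against that stands a model with several covariance components at n of about 20, where a poor choice costs more than the 1.2–1.4% of standard error to be gained. Keeping the planned ANCOVA is a fair trade-off.

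The exclusion is openly disclosed with diagnosis, round and arm. The unstated analysis set and missing-data rule are details that an analyst would fill in when reporting, with missing visits counted by sequence and outcome.

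This rests on assumed variance shares, on completers split 10/10 or 11/9, and on the other 20 patients being complete. The documents neither contradict nor expressly confirm the last point. If many visits proved to be missing, the balance would need another look.

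### Both ANCOVAs treat the pre-stimulation T0 as an outcome level of TIME, so the TREATMENT main effect is diluted and loses power; testing it over T1–T3 adjusted for T0 is a cheap improvement

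*Combined protocol and SAP*

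**What the plan says.** Statistical Analyses specifies, for the clinical scores, a "two-way repeated measure ANCOVA with TIME (T0, T1, T2 and T3) and TREATMENT (sham vs real stimulation) as within-subjects factors", and for CBI a "three-way repeated measures ANCOVA with TIME (T0, T1, T2 and T3), ISI (3, 5, 10 ms) and TREATMENT (sham vs real stimulation", again with every factor varying within the patient. In both, the only covariate is the order of the two stimulations. The section describes no change score, no baseline covariate and no constraint on the baseline means.

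Under Study design, T0 comes before stimulation, and it is measured again in the second period: after crossing over, patients "underwent the same standarized assessment as in the first phase, at baseline, at two-weeks post-stimulation, at one-month and at three-months". Every patient who completes both periods thus has two T0 values for each clinical score and for CBI at each ISI.

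Under Participants, the trial enrolled "Twenty-one patients with neurodegenerative ataxia", and "One patient with MSA-C dropped out from the study during the first round (sham stimulation) and was not considered in the present analysis", which leaves 21 − 1 = 20 analysed. The sample size "was assessed using a power analysis, from results obtained from previous studies", but no inputs to that calculation are reported.

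**The concern.** T0 cannot be affected by the stimulation that follows it. As a fourth level of TIME it still enters the TREATMENT main effect with the same weight as each post-stimulation visit. This has two consequences. A true effect at T1–T3 is averaged with an expected zero. And if a patient happens to score worse before real than before sham stimulation, that difference is carried into the treatment estimate, although the data to correct for it have been collected.

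The same structure governs SARA, ICARS, 9HPT, 8MW, SF-36 and CBI. A main effect is also the kind of term the plan uses to open its post hoc comparisons. With 20 patients, what is at stake is the chance of detecting a true effect, not the false-positive rate.

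**Working it through.** **The plan's own figure.** The sample size cannot be reproduced, because alpha, power, effect size, SD and correlation are not given. Only the relative performance of the tests can be examined, under stated assumptions.

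**Inputs from the documents.** 20 analysed patients; two sequences, allocated "in a 1:1 ratio respectively"; four visits per period; sequence as covariate.

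**Assumptions.** Ten patients per sequence. Let D_t be a patient's real-minus-sham difference at visit t, with SD 1 and common correlation rho between visits. Expected D is 0 at T0 and 0.70, 0.49, 0.28 at T1, T2, T3 (a fading effect). Two-sided 5%.

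**What each test measures.**

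1. TREATMENT as planned tests the mean of D_0 to D_3. Its expected value is (0 + 0.70 + 0.49 + 0.28)/4 = 0.3675, against 1.47/3 = 0.49 over T1–T3, which is three quarters. Its variance per patient is (1 + 3rho)/4.
2. TIME x TREATMENT has three degrees of freedom. The sum of squared deviations of the four expected values from their mean is 0.8085 − 4 × 0.3675² = 0.2683, with variance 1 − rho.
3. TREATMENT adjusted for T0 regresses the mean of D_1 to D_3 on sequence (−1/+1) and D_0, and tests the intercept. The expected value is 0.49 and the residual variance is (1 + 2rho)/3 − rho² = (1 − rho)(1 + 3rho)/3.

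**Noncentrality at rho = 0.5, n = 20.**

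- TREATMENT as planned: 20 × 0.3675²/0.625 = 4.32 (1 and 18 df)
- TIME x TREATMENT: 20 × 0.2683/0.5 = 10.73 (3 and 54 df)
- TREATMENT adjusted for T0: 20 × 0.49²/0.4167 = 11.52 (1 and 17 df)

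The ratio of the third to the first is 11.52/4.32 = 2.67. In general it is 4/[3(1 − rho)]: 1.33 at rho 0, 1.90 at 0.3, 4.44 at 0.7, ignoring the one degree of freedom spent.

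**Simulated power, fading effect (4,000 runs per setting; Greenhouse–Geisser for the interaction).**

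| Correlation | TREATMENT as planned | TIME x TREATMENT | TREATMENT, T1–T3, T0-adjusted |
|---|---|---|---|
| Equal, 0.3 | 61% | 57% | 85% |
| Equal, 0.5 | 49% | 74% | 88% |
| Equal, 0.7 | 44% | 93% | 94% |
| Autoregressive, 0.3 | 71% | 48% | 83% |
| Autoregressive, 0.5 | 58% | 58% | 79% |
| Autoregressive, 0.7 | 47% | 79% | 83% |

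With no true effect and equal correlation 0.5, the three tests reject in 5.1%, 3.6% and 5.2% of runs.

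**Short-lived effect, 0.70/0.20/0, equal correlation 0.5.** The mean over T1–T3 is 0.30 and over T0–T3 is 0.225. Noncentrality is 20 × 0.225²/0.625 = 1.62 for TREATMENT as planned, 20 × (0.53 − 4 × 0.225²)/0.5 = 13.10 for TIME x TREATMENT, and 20 × 0.30²/0.4167 = 4.32 for the adjusted TREATMENT test. Simulated power is about 83% for the interaction and 47% for the adjusted test. Adjustment still improves on the planned main effect, but the interaction is clearly the better test here.

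**The case against.** A reader might infer that the collected baseline is never used. The models do not support that. TIME x TREATMENT compares changes from T0 between real and sham, subtracting T0 with a fixed weight of 1. The stated aim is the effect of treatment on scores over time, and the interaction is the natural term for it. The large contrast (49% against 88%) is with the main effect only.

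A reader might also infer that the T0-adjusted mean over T1–T3 should replace the interaction. That does not follow either. The primary question covers both short- and long-term benefit, so an early effect that vanishes is a live possibility, and for it the interaction wins by 83 − 47 = 36 points in the example above. Very high correlation can also favour the interaction: at autoregressive correlation 0.8 with the fading effect it has 92.5% against 88.8%.

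At the other extreme the covariate itself adds nothing. With rho = 0 and a constant effect of 0.5 SD, the T1–T3 mean has 95.5% power without T0 and 94% with it, so the gain over the planned 89% comes only from taking T0 out of the outcome. The two T0 visits are more than six months apart, so a low rho is possible.

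Finally, the period-2 T0 follows period-1 treatment. It comes "After a wash-out period of three months after the last visit", but residual benefit would distort any adjustment for it. That stands as an assumption to be stated. It does not favour the current plan, whose interaction subtracts the same T0 and whose main effect averages it in.

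None of this rescues the TREATMENT main effect as specified: the adjusted version was more powerful in every effect shape and correlation tried, with rho from 0 to 0.9.

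**Conclusion.** The point holds as an efficiency loss that concerns mainly the TREATMENT main effect. Under the fading-effect assumptions with equal correlation, moving T0 from outcome to covariate raises that test's power by 24, 39 and 50 points at rho 0.3, 0.5 and 0.7. Against the better of the two planned terms the gain is 24, 14 and 1 points, and it reverses for a short-lived effect. These sizes rest on an assumed rho and effect shape that the documents do not give, and no simulation was run for the three-way CBI model.

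The documents do not support reading this as bias or as an inflated false-positive rate: the planned tests hold their 5% level. Nor do they show that the trial as a whole was underpowered, since the inputs to the sample size are not reported. This is a cheap improvement, not a defect that invalidates the analysis.

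**What to change.** In Statistical Analyses:

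1. Test the TREATMENT main effect over T1–T3 only. Take each patient's mean real-minus-sham difference over those visits, regress it on sequence (coded −1/+1) and the real-minus-sham difference at T0, and test the intercept. Do not mean-centre the T0 difference, because that takes the adjustment out of the estimate.
2. Keep TREATMENT by TIME as a formal test, not just a description of fading. Use either the planned TIME x TREATMENT over T0–T3 or a T0-adjusted joint test of real against sham at T1, T2 and T3.
3. State beforehand how the two tests share the 5% error.
4. For CBI, average the follow-up differences and the T0 difference over the three ISIs for the TREATMENT test, and match T0 by ISI for ISI-specific comparisons.
5. State the assumption that the period-2 T0 carries no residual period-1 effect.

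The cost is revised wording and a short change to the analysis syntax, with no new data. The adjusted test has 17 residual degrees of freedom instead of 18. The covariate brings little or nothing if rho is near zero, and item 2 is what guards against losing power for a short-lived effect.

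### Sequence enters both repeated-measures ANCOVAs as a covariate with no stated coding; if it was left uncentred, the treatment tests lose power and can be biased by a period effect

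*Combined protocol and SAP*

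**What the plan says.** The design is a two-period cross-over. Under Study design, patients receive real stimulation "or sham stimulation for 5 days/week for 2 weeks, in a 1:1 ratio respectively". The second period is described as follows: "After a wash-out period of three months after the last visit (i.e., T3), each patient received the opposite treatment (cross-over phase".

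Statistical Analyses gives two models. The clinical-score model has TIME and "TREATMENT (sham vs real stimulation) as within-subjects factors, and the sequence in which stimulation was performed (real-sham vs sham-real) as covariate". The CBI model adds ISI and otherwise repeats the form: "TREATMENT (sham vs real stimulation) as within-subject factors, and the sequence in which stimulation was performed (real-sham vs sham-real) as covariate". TIME runs from T0 to T3 within one treatment phase, so it does not represent period. The section gives no numeric code for sequence, no centring, no period term and no model syntax; it names only the software.

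Post hoc comparisons at time points or ISIs follow "When a significant main effect was reached".

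On numbers, the Participants section reports 21 patients entered and states: "One patient with MSA-C dropped out from the study during the first round (sham stimulation) and was not considered in the present analysis". That leaves 20 analysed. The split by sequence is not given.

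**The concern.** In a standard repeated-measures ANCOVA the covariate has its own slope for each repeated measure. The TREATMENT test is then the test of the intercept when each patient's real-minus-sham contrast is regressed on the covariate, and the slope on sequence carries the period effect. The intercept is the fitted contrast where the covariate equals zero. For a two-level label that point is arbitrary:

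- With a symmetric code or a between-subjects factor, it is the average of the two sequences, which is what a cross-over should estimate.
- With 0/1, it is one sequence only.
- With 1/2, it lies outside the data.

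Two things are at stake. Precision falls under either uncentred code even if the periods do not differ. If they do differ, the TREATMENT estimate is also biased, in a direction set only by which sequence has the lower code. A difference is plausible, because three months to T3 plus a three-month wash-out puts the period starts about six months apart in a neurodegenerative disease. On the section's wording, the main-effect test also helps decide which post hoc comparisons are made.

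**Working it through.** There is no figure in the plan to reproduce: the power analysis is mentioned without its inputs.

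**Inputs from the documents.** 21 patients, 1:1 allocation, one first-period sham drop-out, 20 analysed. If allocation was as even as possible (11+10 or 10+11), removing one sham-first patient leaves 11 real-first and 9 sham-first, or 10 and 10.

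**Assumptions.** Two-sided alpha 0.05; sigma is the SD of a patient's real-minus-sham contrast D, set to 1; delta of 0.1, 0.25 or 0.5; tau of 0 or 0.662, the latter chosen to give 80% power under the symmetric code.

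**Estimand.** E(D) is tau + delta in real-sham and tau - delta in sham-real. Let a be the mean of D in the lower-coded sequence and b the mean in the other. The fitted line at covariate zero is:

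- -0.5/+0.5 or factor: (a + b)/2, with expectation tau.
- 0/1: a, with expectation tau ± delta.
- 1/2: 2a - b, with expectation tau ± 3 delta; for example 2(tau + delta) - (tau - delta) = tau + 3 delta.

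**Precision at 10:10.** The variances are (1/10 + 1/10)/4 = 0.05, 1/10 = 0.10, and 4/10 + 1/10 = 0.50. The SEs are 0.224, 0.316 and 0.707, so the ratios to the factor are 1.41 (0/1) and 3.16 (1/2).

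**Precision at 11:9.**

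- Factor: (1/11 + 1/9)/4 = 0.0505, SE 0.225.
- 0/1: 1/11 or 1/9, SE 0.302 or 0.333.
- 1/2: 4/11 + 1/9 = 0.475 or 4/9 + 1/11 = 0.535, SE 0.689 or 0.732.

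The first value applies when the group of 11 has the lower code.

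**Rejection rates for TREATMENT** (noncentral t, 18 df, 10:10):

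| Case | Factor or ±0.5 | 0/1 | 1/2 |
|---|---|---|---|
| Power, tau = 0.662, delta = 0 | 80% | 51% | 14% |
| Type I error, delta = 0.1 | 5% | 6% | 7% |
| Type I error, delta = 0.25 | 5% | 12% | 17% |
| Type I error, delta = 0.5 | 5% | 32% | 52% |
| Rejection, tau = 0.662, delta = 0.25 | 80% | 78% or 23% | 47% or 5% |

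In the last row the two values differ only in which sequence has the lower code. At 11:9 with delta = 0, power is 80% (factor), 55% or 47% (0/1), and 15% or 14% (1/2).

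**TREATMENT x TIME** (40,000 simulated trials, 10:10, independent visit noise with SD 1, three orthonormal time contrasts of D, F on 3 and 54 df). Results are for factor, 0/1 and 1/2 in turn:

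- Power for a sustained effect of 1.3: 83%, 51%, 13%.
- Type I error with a constant period shift of 1: 5%, 5%, 5%. The shift cancels from the time contrasts.
- Type I error with a post-baseline gain 0.4 larger in period 1: 5%, 9%, 12%.
- The same with a gain 0.8 larger: 5%, 21%, 36%.

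**Additive reading.** If sequence enters only as a between-patient term, it leaves the within-patient tests untouched and the period effect stays in the error. A one-sample t test on D with n = 20 (100,000 simulated trials) gives type I error of 3-5%. Power at 10:10 is 78% at delta = 0.25 and 73% at delta = 0.5. At 11:9 the mean of D is (11(tau + delta) + 9(tau - delta))/20 = tau + 0.1 delta, and power at |delta| = 0.5 is 65-79%.

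**The case against.** The strongest reply is that no uncentred code is shown. The text names two categories and calls sequence a covariate. That does not rule out a between-subjects factor or a symmetric code, and under either there is no problem. It is also a premise that the covariate interacts with the within-subject factors, since no syntax is given. This stands: the point is an under-specification with a conditional consequence, not a demonstrated error in results.

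Second, the lack of a named period term is not a separate fault. In the usual model sequence x TREATMENT carries period, so period is adjusted for if the code is right. This also stands.

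Third, the aim concerns change over time and T0 precedes stimulation, so TREATMENT x TIME is the more natural test, and a constant period shift does not inflate it. That is correct, and the larger error rates for that test need a sizeable period-by-time effect that the documents do not quantify. The loss of power in TREATMENT x TIME remains.

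Fourth, a falsely significant main effect need not lead to false time-point claims, because the post hoc tests are Bonferroni-corrected. A simulation at 10:10 assumed no treatment effect, a constant period shift, visit correlation 0.5 and paired tests at four time points. A false TREATMENT result followed by any significant post hoc test occurred in about 1.1-1.3% of trials (0/1) and 0.4-1.2% (1/2), against 1.6-2.4% with a factor, for delta from 0 to 0.5 sigma. So under those assumptions the false-positive harm lies in the main-effect test if it is reported on its own, while the power loss can keep post hoc comparisons from being made at all.

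**Conclusion.** The concern holds as a conditional one. Both models leave open a choice that determines what the treatment tests estimate, and a reader cannot tell which analysis was run. With sequence as a factor or coded symmetrically, nothing is lost. With an uncentred 0/1 or 1/2 covariate, the SE rises 1.41-fold or 3.16-fold at an even split whether or not the periods differ, and TREATMENT is biased by delta or 3 delta when they do. The power loss follows from the coding and a near-even split; the bias and false-positive figures rest on assumed values of delta. The additive reading costs modest efficiency and does not inflate false positives. The point should be fixed. Confidence is medium, because the coding actually used is unknown.

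**What to change.** State how sequence was coded and how many patients were analysed per sequence. In both models, enter sequence as a between-subjects factor, or code it -0.5/+0.5, and report TREATMENT x SEQUENCE, and its interaction with TIME, as the period effect. Mean-centring is almost enough, but at 11:9 it leaves a bias of 0.1 delta.

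An equivalent route is a linear mixed model with treatment, period, time, treatment x time and period x time as fixed effects and patient and patient-by-period as random effects, adding ISI and its interactions for CBI.

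If an uncentred covariate was used, rerun the treatment tests and the post hoc comparisons that depend on them. The cost is a sentence in the plan and one changed model statement per model. No new data are needed, and nothing is lost if the coding was already symmetric.
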